2. SUMMARY

TITLE: Effectiveness of Percutaneous Electrolysis Application on Muscular Scar Tissue.

JUSTIFICATION: The significant advancements in invasive physiotherapy have led to the exploration of new treatment approaches for certain pathologies. In this case, percutaneous electrolysis appears to show promising results in the recovery of muscle injuries, which is why this line of research has been pursued in this study.

OBJECTIVE: To determine the effectiveness of an intervention involving the application of percutaneous electrolysis at different doses compared to a simulated intervention in adults with a muscle tear in the medial gastrocnemius.

MATERIALS AND METHODS: Approximately fifty adults with a muscle tear in the medial gastrocnemius will be included in this study. The first group will

APPLICABILITY OF EXPECTED RESULTS: The results of this study aim to provide valuable information regarding the effects of percutaneous electrolysis on muscle tears, improving the management of such injuries. Furthermore, this work seeks to contribute to the knowledge base on the use of percutaneous electrolysis by applying two different protocols with varying intensity and application time. This approach will provide insights into the treatment, management, and prognosis of muscle injuries addressed through invasive physiotherapy, specifically percutaneous electrolysis.

3. JUSTIFICATION

The completion of this research work is due to several reasons explained below.

We currently live in a society that, thanks to social and educational policies, increasingly places more importance on physical activity regardless of age. This situation leads to an increase in the incidence of sports-related injuries. There are many situations in which the muscular system of the body is put to use.

This makes it a tissue susceptible to injury. This type of pathology can have a good prognosis in individuals with a good repair capacity, however, in others it can cause problems, such as a higher risk of re-rupture, and long-term discomfort. (1)

The study of musculoskeletal injuries has been around for a long time, but it has not been until the last decade that there has been an exponential increase in research in this field. The physical preparation of athletes is increasingly more demanding, although muscle injury continues to be a problem at all levels, being one of the most prevalent pathologies in the world of sport. The bibliography regarding injury to this tissue proposes many action protocols, especially in acute stages, but more research is needed in more chronic stages.

Consulting this bibliography, we found some authors such as José Manuel Ibáñez, who, together with his collaborators, investigate the therapeutic potential of Percutaneous Electrolysis (PE) in musculoskeletal pathology, more specifically in chronic injuries. (2,3,4,5,6)

In most of their publications, they studied its effect on tendon pathologies, finding that percutaneous intratissue electrolysis in tendon tissue could have neutralizing effects on the injury, "cleaning" the area and promoting the arrival of repairing substances to it. Currently, there are several published articles that have studied the effects of this technique when a muscle-tendon injury occurs, both at the histological and functional level, obtaining both satisfactory results in terms of its early application. (2,3,4,5,6,7,8,9,10)

The question that we were asking ourselves at this time in relation to the data obtained from this bibliography is whether this same technique would be used in injuries that have not had an optimal recovery process and whose tissue does not have the initial characteristics, but more specifically, those of a fibrotic scar. In normal situations, the muscle-tendon tissue has innate regenerative capacities thanks to satellite cells after an injury (11,12,13,14). These cells, once the injury has occurred, are activated to regenerate the tissue, returning practically all the properties it had. On the contrary, these functions decrease with age.

aging, pathology or disease and spontaneous healing is not complete and the result is an area with a tissue quality very different from that before the injury resulting in a fibrotic scar (15).

The processes that occur in this incomplete recovery are several and to this day it has not been clearly clarified why and what are the mechanisms by which it occurs (12,16,17). That is why understanding the optimal management of these injuries is essential to restore the level of function prior to the injury, as well as to return values such as strength, joint range or risk of complications (**Mistake! Reference source not found.**,17).

For the reasons stated above, it has been decided to pursue this line of research by carrying out the project entitled "EFFECTIVENESS OF THE APPLICATION OF PERCUTANEOUS INTRA-TISSUE ELECTROLYSIS IN MUSCULAR SCAR TISSUE"

4. OBJECTIVES

RESEARCH QUESTION:In adults with medial gastrocnemius injury, how effective is percutaneous electrolysis in terms of pain, kinesiophobia, fatigue and mobility?

HYPOTHESIS:The working hypothesis of the present study is the following: "The application of percutaneous electrolysis (PE) at high intensity (3 mA) and at low intensity (0.3 mA) will be more effective in the treatment of muscle tears of the internal calf than the simulated application of percutaneous electrolysis in adult subjects."

GENERAL OBJECTIVE:To determine the effectiveness of an intervention consisting of the application of percutaneous electrolysis in different doses versus the application of a simulated intervention in adults who present a muscle tear in the internal calf.

SPECIFIC OBJECTIVES:

- 1. To analyze the effectiveness of Percutaneous Intratisular Electrolysis, in its different forms. intensities, applied to the internal gastrocnemius muscle, in terms of myofascial pain in patients participating in the study, both at rest and during muscle contraction, measured using the visual analog scale (VAS).
- 2. To analyze the effectiveness of a simulated intervention applied to the internal gastrocnemius muscle, in terms of myofascial pain in patients participating in the study, both at rest and during muscle contraction, measured through the visual analog scale (VAS).
- 3. Evaluate and compare the effect of the protocols on the level of kinesiophobia of the participating subjects through the TSK-11SV questionnaire.
- 4. To demonstrate whether there are differences in muscle fatigue of the affected muscles of the participants in both groups.
- 5. To objectively determine the degree of range of ankle dorsiflexion mobility with full knee extension of the patients participating in the study.

5. MATERIAL AND METHODS

A) TYPE OF STUDY

This doctoral thesis consists of a study which is defined as a randomized, experimental and controlled clinical trial, with three parallel groups, prospective, longitudinal and with a blind evaluation for the researcher.

B) MATERIALS AND/OR TECHNIQUES USED

Regarding the materials / physical resources necessary to carry out this study, they are stated below.

- Room at the Miguel Naranjo Center for the first consultation and different evaluations.
- Office with a stretcher and the equipment required for a physiotherapy consultation.
- Certified medical device (EPI Alpha, Barcelona, Spain)
- Needles for the application of the EP technique.
- Ultrasound

As for the techniques used, different ones will be used for each study group and are developed below.

1. Working methodology of the High Intensity Percutaneous Electrolysis group.

A sterile, disposable stainless steel needle of different lengths depending on the area to be treated will be connected to the EP device. The gauge of these needles will be 0.25 mm. A current of 3 mA will be applied 3 times for a duration of 3 seconds each. To avoid bias, the technique will be performed for 90 seconds, just like the low-intensity treatment group, and in the last 20 seconds the current will be applied with the parameters described above. Three sessions will be applied divided into 3 consecutive weeks. This parameter has been previously used in recent studies (10,20).

2. Working methodology of the low intensity percutaneous electrolysis group

This technique will be performed with the same instrument as the high intensity technique. It differs from the previous treatment group in that the current intensity in this case will be 0.3 mA for 90 seconds. Similarly, 3 sessions will be applied divided into 21 consecutive days (21,22).

3.Simulated Percutaneous Electrolysis working methodology.

The needle and the EP device will be connected in the same way as for the other treatment groups. The needle will be inserted without reaching the lesion area and the characteristic sound of turning on the EP machine will be made. It will last 90 seconds and at no time will the galvanic current be applied. The same aseptic precautions will be applied, in addition to the same final hemostasis guidelines and the same post-treatment guidelines provided to all the other subjects in the study.

C) STUDY POPULATION

The study population for this clinical trial will be completed by a sample of approximately 50 adults between the ages of 18 and 65 who have suffered a muscle injury in the medial gastrocnemius. The researchers will consider a tear in the medial gastrocnemius if this pathology had any of the following characteristics:

- Medical diagnosis of fibrillar tear in the inner calf.
- Physiotherapeutic diagnosis of muscle tear after ultrasound examination.
- Pain in the GM area that coincides with a previously diagnosed fibrillar tear.

Theinclusion criteria for the following study will be the following:

- Age over 18 years and under 65 years.
- Muscle tear in the medial gastrocnemius.
- With pain in the area of the injury.

- That you have been informed of the purpose, as well as the risks and benefits of this study and that you have provided your written consent to participate in the trial.
- Available for tracking.

The exclusion criteria are listed below:

- Active rehabilitation in other musculoskeletal pathology.
- Belenophobia
- Immunosuppression.
- Uncontrolled metabolic diseases.

D) STUDY VARIABLES:

1. Sociodemographic variables

- 1. Age (years).
- 2. Sex.
- 3. Weight (kg).
- 4. Height (m).
- 5. Tear size (cm)
- 6. Location, Since the medial gastrocnemius is a peripheral myoconnective region, we will distinguish between tendon, myotendinous, muscular and myofascial injuries (23).
- 7. Chronicity: This section sets out the time since the rupture occurred. It is considered to be part of the 2nd week if it occurred before 14 days, 3rd week if it occurred before 21 days, 4th week if less than 28 days have passed, and between 4 and 8th week if less than 56 days have passed.

2. Outcome variables.

1. EVA pain scale.

The evaluation of the pain of the participants both in an upright position (without contraction) and in contraction will be carried out through a Verbal Scale

Pain score of 10 points (0 = no pain, 10 = maximum tolerable pain). Subjects will be asked to numerically rate the pain in a neutral standing position and in a position with both heels raised, also commonly known as standing on their toes. In the latter position, a score of 10 will be given if the subjects are unable to maintain this position for at least one full lift.

2. Kinesiophobia questionnaire (TSK-11SV).

Recovery from painful injuries is associated with fear of movement, also known as kinesiophobia (24). It could be defined as an irrational or excessive fear of movement due to fear of injury or re-injury. For this reason, a kinesiophobia questionnaire (annex II) will be provided at the beginning of the study (day I, evaluation and first intervention) to all participants to assess kinesiophobia of performing certain movements that may cause pain or worsen previous injuries. It consists of 11 questions with a minimum score of 11 and a maximum of 44.

3. Ankle dorsiflexion range with the knee straight.

The evaluation of this variable will be carried out by measuring the angle obtained from the dorsiflexion of the ankle with a knee extension. This stretch is commonly performed in sports practice, so patients are generally already familiar with it...Stretching will be done with participants barefoot.. Likewise, participants will be instructed on how to place the test.. The leg to be tested was positioned so that the foot was placed on the midline of an area marked on the floor, and the foot of the healthy leg was placed forward at a distance of one step. The end point of the gastrocnemius stretch was defined as the point at which participants felt discomfort without lifting the heel and without pelvic rotation. Patients would place their hands against the wall for balance and would be asked to maintain the extended position of the hip and knee joints during the stretch (25).

. .

During the stretch, participants will be instructed to reach a pain or discomfort level of 7 or greater on a scale of 0 to 10 and therefore to hold the stretch at approximately this perceived intensity.

A digital camera (Canon EOS 2000D 24.1 MP) will be placed on the ground at a distance of 2 meters perpendicular to the plane of movement of the right leg to record the standing ankle dorsiflexion angle. The ankle joint angle in stretching will be analyzed by reflective markers placed on the knee (fibular head), ankle (external malleolus) and fifth metatarsal (head) and calculated by free software (RULER- Ergonauts Software. Polytechnic University of Valencia). The maximum standing dorsiflexion is defined as the intersection of a line joining the knee and ankle markers and the horizontal line crossing the heel and fifth metatarsal. (25)

4. Muscle fatigue of the triceps surae.

The assessment of fatigue in this muscle group will be carried out by performing a heel-raise test (4) at the beginning and at the end of the test for all participants who have completed it. The test consists of placing the patient on one leg and with the help of a metronome at a speed of 40 beats per minute (Garmin Fénix 5/5S), he is asked to raise his heel (4). When the patient is unable to raise his heel for 3 consecutive beats, fatigue will be considered. Light support on a wall is authorized to save the patient's balance.

E) WORK PLAN.

[figure not shown]
The study will be carried out as follows;

- Phase I or initial: Pre-study consultations will begin. Any patient who calls the
 centre to express their wish to take part in the study or who comes to the
 centre naturally will be given an appointment for a consultation with the
 principal investigator. All patients who strictly meet the eligibility criteria will
 be offered to participate in the study.
- Phase II or treatment: The entire treatment will be applied by the same physiotherapist (principal investigator) according to the randomization table that will be made so that each patient is assigned a treatment; high intensity EP, low intensity EP or sham EP. The treatment will be carried out in three sessions divided into three

weeks (days 1, 7 and 14) The person in charge of collecting the data will not be aware of which treatment each patient receives and will collect the data before the interventions.

• *Phase III or evaluation:*Patients will be scheduled for appointments two weeks after the last visit (day 28). The data from this last visit will be collected by the same person as the previous ones. All tests will be performed to collect the data and they will be given a telephone number in case they have any adverse events.

Study timeline.

F) ANALYSIS PLAN

For the coding and analysis of the data, the SPSS 22.0 statistical program will be used. For the treatment of quantitative variables, tables of absolute and relative frequencies will be prepared; in the case of quantitative variables, frequency measures will be used to determine their distribution, also obtaining their mean and standard deviation. The Kolmogorov-Smimov test will be performed to check the normality of the distribution. For the comparison of means of the continuous dependent variables, a bivariate statistical analysis will be performed using the Student T test. In the case of ordinal dependent variables, a comparison of medians will be performed using the bivariate analysis applying the Mann-Whitney test. In all cases, a 95% confidence interval and a precision error of 5% will be established.

G) LIMITATIONS AND POSSIBLE BIASES OF THE STUDY

This study has a number of limitations that should be taken into account when designing future research.

Firstly, the sample of participants will include people aged between 18 and 82, which may lead to biases due to the different variables that can influence different ages. It should also be noted that all people who participate will do so voluntarily by calling the centre to ask about the study or by showing up at the centre, so the possibility of bias due to voluntary participation must be taken into account.

It should also be noted that only one follow-up consultation will be carried out two weeks after the last intervention, so we will not have information on the behaviour of the variables beyond that date and therefore we will not be able to analyse the long-term results. It would be interesting to add post-intervention evaluations, as well as to study possible long-term recurrences.

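### Inability to hold the two-heel raise is recorded as pain 10 with nothing to flag it, so a difference in function between arms would be reported as a difference in contraction pain

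*Protocol*

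**What the plan says.** Protocol section 5.D (Outcome variables, pain scale) has participants rate pain on a scale anchored as "0 = no pain, 10 = maximum tolerable pain". They rate it twice: in neutral standing, and "in a position with both heels raised, also commonly known as standing on their toes". For the second position only, "a score of 10 will be given if the subjects are unable to maintain this position"; the threshold is a single complete lift. The rule carries no condition on the pain reported or on why the lift failed.

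The data collection sheet (section 6) gives pain in load one cell before and one cell after the intervention. It has no field for inability.

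Section 4 lists pain (at rest and in contraction), kinesiophobia, fatigue and mobility as separate objectives. Fatigue has its own measurement in section 5.D: "The assessment of fatigue in this muscle group will be carried out by performing a heel-raise test", done on one leg to a metronome, where "When the patient is unable to raise his heel for 3 consecutive beats, fatigue will be considered".

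Section 5.F states: "For the comparison of means of the continuous dependent variables, a bivariate statistical analysis will be performed using the Student T test". It gives Mann-Whitney for ordinal outcomes and does not say to which class the pain score belongs.

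**The concern.** Objective 1 asks about pain during contraction. Under the rule, a participant who fails the lift through weakness, guarding or fear of movement is recorded as having the worst pain on the scale. Such reasons are foreseeable, because section 5.D itself links recovery from painful injury to fear of movement.

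If one arm regains the ability to lift more often than another, the recorded pain scores will differ even where felt pain does not. On the sheet an assigned 10 looks the same as a felt 10, so no later analysis could separate the two. This is a data-collection rule, so a statistical analysis plan could not repair it.

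A second, conditional concern is that a cluster of assigned 10s can widen the spread of the scores. If the scores are compared by means, that can cost power in a trial with few participants per arm.

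**Working it through.** The protocol states no power, SD, expected mean or share unable to lift, so there is no figure of its own to reproduce.

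**Inputs from the Protocol**
- About 50 participants (5.C) in three parallel groups (5.A): 50/3 = 16.7, taken as 17 per arm. Equal allocation is assumed.
- 95% confidence (5.F), taken as two-sided 5%.

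**Assumptions**
- SD *s* = 2 among those able to lift, with mean *m*.
- Share unable *p*.
- Mean felt pain *f* among those unable: the same as the others, about 7, or about 9.

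**1. Function reported as pain**

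Scored mean = (1 − p)m + 10p. Felt mean = (1 − p)m + pf. The rule therefore adds p(10 − f) to an arm. With the same *f* in both arms, the artefact between arms is (p₂ − p₁)(10 − f).

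With m = 3 in both arms and 5% v 20% unable:
- f = 3: 0.15 × 7 = 1.05
- f = 7: 0.15 × 3 = 0.45
- f = 9: 0.15 × 1 = 0.15

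Simulation with whole-number scores limited to 0–10 gives 1.04 for f = 3. For f = 9 the scored difference is 1.04 against a felt difference of 0.88, an artefact of 0.16. In the first case there is no felt difference at all, yet a t test rejects about 16% of the time instead of 5%.

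**2. Variance and power, if pain is compared by means**

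Scored variance in an arm = (1 − p)s² + p(1 − p)(10 − m)². Take felt means 3 v 5 and p = 0.10 in both arms:
- Arm with mean 3: 0.9 × 4 + 0.09 × 49 = 8.01, SD 2.83
- Arm with mean 5: 0.9 × 4 + 0.09 × 25 = 5.85, SD 2.42
- Pooled SD = √[(8.01 + 5.85)/2] = 2.63
- Difference in means = 0.9 × 2 = 1.8
- Noncentrality = 1.8 / (2.63 × √(2/17)) = 1.99, so power is about 0.49 on 32 df

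Without the rule, and with those unable feeling the same pain as the others, noncentrality is 2 / (2 × √(2/17)) = 2.92 and power is about 0.80. At 5% and 15% inability the scored power is about 0.62 and 0.39.

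The scored result does not depend on what those unable actually feel, but the felt-pain result it should be compared with does:
- Same pain as the others: 0.80 against 0.62, 0.49 and 0.39, a cost of about 18 to 41 percentage points.
- About 7: a cost of about 10 to 18.
- About 9 (SD 1): power on felt pain is already only about 0.66, 0.53 and 0.45, so the cost is about 4 to 6.

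**3. The direction is not fixed**

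If able and unable participants both feel 8, scored variance at p = 0.30 is 0.7 × 4 + 0.21 × 4 = 3.64, SD 1.91 against 2.00. The spread shrinks.

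Unequal inability can raise apparent power. With felt means 5 v 4, and those unable feeling the same as the others in their arm, power on felt pain is 0.30. On the scored values it is 0.13 with 20% unable in both arms, 0.33 with 20% v 10%, and 0.50 with 20% v 5%. The gain in the last two cases is function counted as pain.

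**The case against.** **The t test is not fixed for pain.** Section 5.F leaves open whether a 0–10 verbal score is continuous or ordinal, and that choice is commonly left to a statistical analysis plan. Under Mann-Whitney an assigned 10 is simply a tied worst rank. This stands, so a reader should not infer that the rule necessarily inflates the variance of a mean-based test. Ranks do not remove the mixing, however. If inability is unrelated to felt pain, Mann-Whitney with no pain difference still rejects about 11% of the time at 5% v 20% inability and 23% at 5% v 30%. With felt means 3 v 5 and equal inability of 5%, 10% and 15%, its power falls from about 0.77–0.78 to 0.68, 0.57 and 0.46.

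**Those who cannot lift probably hurt more.** Every participant enters with pain at the injury (section 5.C), so felt pain near the top of the scale is plausible in this subgroup and most of the loss then disappears. This also stands, and is why the size must be given as a range.

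**Inability may be rare.** The raise uses both heels, so the sound leg can help. At 2% inability, 0.02 × 50 = 1 participant. The protocol gives no figure either way.

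**Double counting.** A reader might infer that the heel-raise test already captures the same inability. The documents do not support that: the pain rating uses a two-heel raise, while the fatigue test is a single-leg, metronome-paced endurance task. Failing the second does not show whether the first was possible.

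**A worst score avoids missing data.** Someone who never reaches the position has no true contraction rating, and a rating from an aborted attempt may be too low. That supports keeping a worst-score analysis, but not storing it unmarked as measured pain.

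**Conclusion.** The point holds for meaning and record-keeping. The rule puts failed function on the pain scale at its maximum, and the sheet cannot distinguish assigned from felt scores, so objective 1 cannot be answered cleanly for contraction pain if inability differs between arms. Pain at rest is not touched.

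The variance claim holds only conditionally: pain must be analysed by means, felt pain must not already be near the ceiling, and the share unable must be moderate. A reader might take the fall in power from 0.80 to as low as 0.39, or a spurious difference of a full point, as the expected effect. Both need those unable to feel no more pain than the others. If they feel about 9, the cost is about 4 to 6 percentage points of power and the artefact is about 0.16 points. All these figures rest on assumed means, SD, inability shares and equal arms of 17, none of which the protocol supplies.

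**What to change.** - On the sheet, at each time point, record the pain felt on the attempted raise and add a yes/no field for being unable to complete one full lift.
- Compare felt pain between arms for objective 1, and report the number unable by arm.
- If the score with inability set to worst is kept, name it a combined pain and function score, analyse it by ranks, and show it beside the felt-pain analysis.

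The cost is one tick box per assessment and a few more lines of results. The downside is that a rating from an aborted attempt may understate pain, which is the reason to show both analyses. The change needs to be in place before data are collected, because ratings that were replaced by 10 cannot be recovered from the sheet.

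### The heel-raise fatigue outcome is limited to participants who completed the trial (or possibly the test), so its day-28 comparison is conditioned on an event after randomisation

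*Protocol*

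**What the plan says.** Protocol section 5.D, outcome variable 4 (muscle fatigue of the triceps surae), has the heel-raise test performed "at the beginning and at the end of the test for all participants who have completed it". None of the other three outcome variables (pain, kinesiophobia, ankle dorsiflexion) carries a completion condition. The kinesiophobia questionnaire, for example, is given at the start "to all participants to assess kinesiophobia of performing certain movements that may cause pain or worsen previous injuries".

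The heel-raise test is done on one leg to a metronome, and its end point is defined by failure: "When the patient is unable to raise his heel for 3 consecutive beats, fatigue will be considered". The protocol does not say what is recorded for someone who cannot raise the heel at all. The data collection sheet (section 6) has a box for a test score before and after the intervention, without a unit.

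For pain on standing on the toes (outcome variable 1), inability has a rule: "a score of 10 will be given if the subjects are unable to maintain this position for at least one full lift".

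The final assessment is at day 28, two weeks after the third session, and there "All tests will be performed to collect the data" (section 5.E). The design is randomised "with three parallel groups, prospective, longitudinal and with a blind evaluation for the researcher". Objective 4, which this outcome serves, is "To demonstrate whether there are differences in muscle fatigue of the affected muscles of the participants in both groups". The analysis plan (section 5.F) names the Student t test for continuous outcomes and the Mann-Whitney test for ordinal ones. It says nothing that brings non-completers back for this outcome.

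**The concern.** Randomisation makes the arms comparable for everyone allocated. It does not make them comparable within a subset formed later by an event that treatment may influence. Completing the trial by day 28 is such an event, and so is being able to do the heel-raise test at day 28. If people with poor recovery leave one arm more often, or if recovered people in one arm stop attending, the remaining participants are no longer a like-for-like comparison.

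A fatigue measure is particularly exposed, because those missing may be the most fatigued. Inability is also foreseeable: the pain rule already expects that some participants cannot manage one lift on both heels, and the fatigue test uses one leg.

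The arms are small. About 50 participants over three arms is 50 / 3 = 16.7, or about 17 per arm if allocation is equal (the ratio is not stated). Each person excluded is then 1 / 17, about 6% of an arm.

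**Working it through.** The protocol gives no figure to reproduce on this point: no effect size, standard deviation, dropout rate or inability rate. The check is therefore of the wording first and of the mechanism second. **Every rate, mean and SD below is an assumption.**

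**1. The wording.** The sentence has the heel-raise test performed at the beginning and end of something also called a test. A test is not performed at the beginning and end of itself, so the second word most naturally means the trial, and the pronoun follows it. That is reading B (completers of the trial). Reading A (completers of the heel-raise test) is less natural but not excluded. The clause also covers the measurement at the beginning. On day 1 nobody has completed the trial, so under reading B the condition can act on that measurement only in retrospect, by setting aside the data of people who later leave.

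**2. Reading B, completers of the trial.** Assume normal scores with SD 8, mean 12 on sham and 16 on active, so the true difference is 4. If people below a threshold t leave with probability p, the mean of those remaining is

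[E(X) - p E(X; X < t)] / [1 - p P(X < t)], with E(X; X < t) = mu Phi(a) - 8 phi(a) and a = (t - mu) / 8.

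Worked case: 60% of sham participants below 10 leave and nobody leaves active. Then a = -0.25, P = 0.401, E(X; X < 10) = 12 x 0.4013 - 8 x 0.3867 = 1.72, and the sham mean is (12 - 0.6 x 1.72) / (1 - 0.6 x 0.401) = 10.97 / 0.759 = 14.4. The difference is 16 - 14.4 = 1.6. A simulation with 2,000,000 per arm gives 1.56, and the other cases as follows:

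| Who leaves | Left sham / active | Difference among completers (true 4.0) |
|---|---|---|
| Unrelated to outcome | 15% / 15% | 4.0 |
| Poor performers, both arms | 15% / 8% | 3.4 |
| Poor performers, sham only | 24% / 0% | 1.6 |
| Poor performers, sham only, stronger | 40% / 0% | -1.2 |
| Recovered participants, active only | 0% / 19% | 1.9 |
| Poor performers, active only | 0% / 14% | 5.7 |

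**3. Reading A, completers of the heel-raise test.** There are two illustrations, with inability scored as 0 raises in the full comparison.

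- *Treatment acts only on ability.* If those able do m raises on average in both arms, the full difference is m x (unable on sham - unable on active), and the difference among the able is 0 by construction. With m = 15 and 25% v 5% unable, this is 15 x 0.20 = 3.0 against 0. With m from 10 to 20, it is 0.5 to 1.0 at 10% v 5% unable, and 3.0 to 6.0 at 40% v 10%, always against 0.
- *Treatment shifts capacity in everyone* (latent mean 8, SD 8, shift 2 or 4 raises, ability cut-off 0, 3 or 5 raises). The full difference of 1.75 to 3.75 becomes 0.97 to 2.81 among the able. The loss runs from 1 - 2.81 / 3.57 = 21% to 1 - 0.97 / 1.81 = 46%.

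**4. Which measurement matters.** Inability on day 1, before the first session, precedes treatment and would not by itself break the randomised comparison. The problem lies in the day-28 value.

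**The case against.** The strongest reply is that the sentence sits among the study variables and says when and in whom a measurement is taken. It is not a definition of an analysis set. A test at the end of a trial can only be done on people who reach the end, the analysis plan states no completers-only rule, and analysis sets and missing-data methods are commonly left to a statistical analysis plan, which is not at hand. This stands in part: the protocol does not declare a completers-only analysis, and the absence of a missing-data method is not the point here. But the protocol does more than stay silent. It writes a completion condition into one outcome and no other. Read literally, the condition also covers the first measurement, and it could exclude someone who missed a session but can still be seen at day 28.

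A reader might also infer that participants unable to lift are certainly dropped. The text does not support that. It needs the less natural reading, and even then someone who fails three beats in a row has arguably reached the test's own end point, with no raises. What is missing is a stated score for that person. For the same reason, the inconsistency with the pain rule exists only under that reading. If the clause means the trial, the two rules answer different questions.

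Finally, a reader might infer that the rule removes the treatment effect. The result of 3.0 against 0 follows directly from assuming equal performance among the able in both arms. If treatment shifts capacity in everyone, part of the effect remains.

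**Conclusion.** The point holds as a badly fixed rule. Under either reading, the day-28 fatigue comparison is conditioned on an event after randomisation that treatment may affect, and nothing in the work plan, the analysis plan or the data collection sheet undoes that condition or scores a participant with no raises. The bias can go in either direction and is nil if non-completion is unrelated to outcome. Its size cannot be derived from the protocol. The range from -1.2 to 5.7 around an assumed true 4, and the 21% to 46% loss under the second reading, show the mechanism and are not estimates for this trial. The protocol does not support saying that the effect is removed, or that the two inability rules plainly contradict each other. The consequence is confined to objective 4 and to one of four outcome variables, but the remedy costs almost nothing.

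**What to change.** Replace the completion clause in section 5.D, outcome variable 4, with wording such as: *for all randomised participants at day 1 and day 28, whether or not they completed all sessions; a participant who attends but cannot perform one raise scores 0.* This assumes that the test score is the number of raises, which the protocol and the data collection sheet should state.

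Three points go with it, here or in the statistical analysis plan:

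- Analyse participants in the arm to which they were randomised.
- Keep a participant with no day-28 visit in the analysis set as missing data. The score of 0 is for people who attend and cannot lift, not for people who are absent.
- Name a rank-based test for this outcome, since section 5.F assigns the Mann-Whitney test only to ordinal variables.

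The cost is one sentence, a unit on the form, and an effort to see at day 28 those who stopped sessions early. The downside is that zeros skew the counts, which is the reason for the rank-based test. The change is cleanest before day-28 data are collected.
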